7.3.1.2.3. Duration of Response

Duration of Response (DOR) is defined, for subjects with a confirmed response (PR or better) as the time between first documented evidence of confirmed response and disease progression or death due to PD, whichever occurs first.

- Duration of response is derived for patients with a confirmed PR or better only.
- Censoring rules will follow those of the TTP analysis.

DOR will be summarized using Kaplan-Meier curves. If there are a sufficient number of progressions or death due to PD among the responders, median DOR, first and third quartiles and 95% CI, will be estimated using the Brookmeyer-Crowley method [Brookmeyer, 1982]. A figure and listing of DOR time will also be provided. Summary and figure of DOR will be based on Part 2 MM population and subgroup: prior anti-cancer therapy of interest; listing of DOR will be based on All Treated MM population.

7.3.1.2.4. Time to Response

Time to Response (TTR) is defined as the time from first dose to the first documented evidence of confirmed PR or better, among subjects who achieve a response (i.e., confirmed PR or better).

TTR will be summarized using Kaplan-Meier method. If data permits, median TTR, first and third quartiles and 95% CI, will be estimated using the Brookmeyer-Crowley method [Brookmeyer, 1982]. A listing of TTR time will also be provided. Summary of TTR will be based on Part 2 MM population; listing of TTR will be based on All Treated MM population.

7.3.1.2.5. Time to Best Response

Time to Response (TTBR) is defined as the time from first dose to the best confirmed response (PR or better), among subjects who achieve a response (i.e., confirmed PR or better).

TTBR will be summarized using Kaplan-Meier method. If data permits, median TTBR, first and third quartiles and 95% CI, will be estimated using the Brookmeyer-Crowley method [Brookmeyer, 1982]. A listing of TTBR time will also be provided. Summary of TTBR will be based on Part 2 MM population; listing of TTBR will be based on All Treated MM population.

7.3.1.2.6. Overall Survival

Overall survival (OS) is defined as the time from the date of first dose until death from any cause. For subjects who do not die, time of death will be censored at the date of last contact.

The protocol is amended to collect long-term survival data (i.e. up to 1 year after last subject completes or discontinues treatment). Subjects who are already completed the study will be contacted to request re-consent.

If all the patients (who were alive at the time of study completion) can be re-consented, OS landmark analysis may be performed at 9 and 12 months using Kaplan-Meier analysis as data permits. A listing of OS will also be provided. The OS landmark analysis will be based on Part 2 MM population; listing of OS will be based on All Treated MM population.

Otherwise, only descriptive analysis (number and % of deaths and lost to follow-up) will be performed.

7.3.1.3. Monoclonal Protein and Serum Free Light Chain

A waterfall plot showing the maximum percent reduction from baseline in Serum M-protein, or Urine M-protein, or difference between two types Serum FLC [Kappa light chain (Kappa LC) and Lambda light chain (Lambda LC)] for each subject will be produced using Part1 and Part 2 MM populations. Only the assessments from the start of treatment up to the start of new anti-cancer therapy will be considered. Only new systemic anti-cancer drugs taken are considered as anti-cancer therapy (radiotherapy and surgeries are not considered as systemic anti-cancer therapy for the purpose of this analysis). The maximum percent reduction will be plotted in the following hierarchical order:

- [1] Plot Serum M-protein maximum percent reduction from baseline if data is available;
- [2] If [1] is not feasible, plot Urine M-protein maximum percent reduction from baseline if data is available;
- [3] If both [1] and [2] are not feasible, plot maximum percent reduction from baseline for difference between two types of Serum FLC if data is available;

Difference between two types Serum FLC

The percent change from baseline for difference between two types of Serum FLC is defined as:

$$(\text{post-baseline difference} - \text{baseline difference}) / \text{baseline difference} * 100\%$$

To calculate the difference, the “involved” and “non-involved” light chains must be determined at first based on the ratio of non-missing values for Serum Kappa LC protein and Serum Lambda LC protein at baseline.

Detailed algorithm is provided as below:

- If the baseline ratio of (Kappa LC/Lambda LC) >1.65 , then Kappa LC is defined as involved FLC, and Lambda LC is defined as non-involved FLC. Then
 - Difference between involved and uninvolved = Kappa LC-Lambda LC
- If the baseline ratio of (kappa/lambda) <0.26 , then Lambda light chain is defined as involved FLC, and Kappa light chain is defined as non-involved FLC
 - Difference between involved and uninvolved = Lambda LC-Kappa LC
- If the baseline ratio of (Kappa LC/Lambda LC) ≤ 1.65 and ≥ 0.26 , then “involved” and “non-involved” FLC can not be determined (ratio is normal), and maximum percent reduction from baseline for difference between two types of Serum FLC won’t be available.

In addition, a scatter plot of free soluble BCMA at pre-dose (cycle 1) and maximum percent change from baseline in Serum M-protein, Urine M-protein or difference between two types Serum FLC will be provided following the hierarchical order specified above.

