Proteasome Inhibitor	5 (5%)	5 (5%)	10 (5%)
BORTEZOMIB	5 (5%)	5 (5%)	10 (5%)
CARFILZOMIB	5 (5%)	5 (5%)	10 (5%)
IXAZOMIB	5 (5%)	5 (5%)	10 (5%)
Chemotherapy	5 (5%)	5 (5%)	10 (5%)
Stem Cell Transplant	5 (5%)	5 (5%)	10 (5%)
Other	5 (5%)	5 (5%)	10 (5%)
Monoclonal Antibody	5 (5%)	5 (5%)	10 (5%)
CXCR4	5 (5%)	5 (5%)	10 (5%)
DARATUMUMAB	5 (5%)	5 (5%)	10 (5%)
ELOTUZUMAB	5 (5%)	5 (5%)	10 (5%)
SILTUXIMAB	5 (5%)	5 (5%)	10 (5%)
HDAC Inhibitor	5 (5%)	5 (5%)	10 (5%)
Not Classified	5 (5%)	5 (5%)	10 (5%)
Immunomodulator and Proteasome Inhibitor	5 (5%)	5 (5%)	10 (5%)

[figure not shown]
This table is summarized per subject level

PPD

Example: POP_F2
Protocol: BMA117159
Population: Part 2 MM

(Data as of: 30MAY2001)

Figure x.xxxx
Plot of Dose Reduction of GSK28557916 by Cycle (Part 2 MM)

[figure not shown]
Doses 1.9 mg/kg and 1.7 mg/kg are combined and represented by 1.7 mg/kg.

PPD

Example: EFF_F1
Protocol: BMA117159
Population: Part 2 MM

Page 1 of 1
(Data as of: 30MAY2001)

Figure 12.0020
Correlation of Free Soluble BCMA at Pre-Dose (Cycle 1) and
Maximum Percentage Change from Baseline
in Serum M-Protein, Urine M-Protein or Serum FLC

Subjid (Treatment) (Type/ Best confirmed Response)
PPD

[figure not shown]
Serum M-protein depicted for subjects with serum M-Protein values;
Urine M-Protein depicted for subjects without serum M-Protein values.
Changes in affected FLC depicted in subjects with no available Serum M-protein values nor Urine M-Protein.

PPD

Example: EFF_F2
 Protocol: BMA117159
 Population: Part 2 MM

Page 1 of 1
 (Data as of: 30MAY2001)

Figure x.xxxxx
 Forest Plot - Overall Response Rate (ORR) (Part 2 MM)

[figure not shown]
[1] Defined as prior CTX regimen with Daratumumab as the only drug in the regimen.
 [2] Defined as prior CTX regimen with Daratumumab and other drugs in the regimen.
 [3] Penta-refractory= refractory to: Bortezomib and Carfilzomib and Lenalidomide and Pomalidomide and Daratumumab.
 [4] A subject is considered as high risk if the subject has any of the following cytogenetics: t(4;14), del17p, t(14;16).

PPD

Example: EFF_F3
Protocol: BMA117159
Population: Part 2 MM

Page 1 of 1
(Data as of: 30MAY2001)

Figure x.xxxx
Profile Plot of Responders (Part 2 MM)

SCR: Stringent Complete Response, CR: Complete Response, VGPR: Very Good Partial Response, PR: Partial Response.

PPD

Example: SAFE_T1
 Protocol: BMA117159
 Population: Part 1

Page 1 of 1
 (Data as of: 30MAY2001)

Table x.xxxx

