- If a subject has neither progressed nor died nor started new anti-cancer therapy, then PFS will be censored at the date of the last adequate assessment defined as an assessment where the Investigator determined response is sCR, CR, VGPR, PR, MR or SD. The date of response will be used as the censoring date.

A summary of the assignments for progression and censoring dates for PFS are specified in Table 5.

Table 5 Assignments for Progression and Censoring Dates for PFS Analysis

Situation	Date of Event (Progression/Death) or Censoring	Outcome Event (Progression/Death) Or Censored
No (or inadequate) baseline tumor assessments ^[1] and the subject has not died (if the subject has died follow the rules for death indicted at the bottom of the table)	First dose date	Censored
No post-baseline assessments and the subject has not died (if the subject has died follow the rules for death indicted at the bottom of the table)	First dose date	Censored
Progression documented between scheduled visits	Date of assessment of progression ^[1]	Event
No progression (or death)	Date of last 'adequate' assessment of response ^[2]	Censored
New anticancer treatment started (prior to documented disease progression or death) ^[3] .	Date of last 'adequate' assessment of response ^[2] (on or prior to starting anti-cancer therapy)	Censored
Death before first PD assessment (or Death at baseline or prior to any adequate assessments)	Date of death	Event
Death between adequate assessment visits	Date of death	Event
Death or progression after an extended loss-to-follow-up time (two or more missed cycles + 7 day window) ^[4]	Date of last 'adequate' assessment of response ^[2] (prior to missed assessments)	Censored

[1] **In part 1**, adequate baseline assessment is defined as at baseline, a patient has at least one of the following measurements: a. Serum M-protein or b. Urine M-protein or c. Serum FLC assay or d. Biopsy proven plasmacytoma (should be measured within 28 days of Screening Visit).

In part 2, adequate baseline assessment is defined as at baseline, a patient has at least one of the following measurements: a. Serum M-protein ≥ 0.5 g/dL (≥ 5 g/L) or b. Urine M-protein ≥ 200 mg/24h or c. Serum FLC assay: Involved FLC level ≥ 5 mg/dL (≥ 50 mg/L) and an abnormal serum free light chain ratio (<0.26 or >1.65) or d. Biopsy proven plasmacytoma (should be measured within 28 days of Screening Visit and no later than the first dose date).

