16.6.3. Efficacy

Laboratory Parameters
Serum M-protein, Urine M-protein, Serum FLC

 • If a laboratory value which is expected to have a numeric value for summary purposes, has a non-detectable level reported in the database, where the numeric value is missing, but typically a character value starting with '<x' or '>x' (or indicated as less than x or greater than x in the comment field) is present, the number of significant digits in the observed values will be used to determine how much to add or subtract in order to impute the corresponding numeric value. 
 ○ Example 1: 2 Significant Digits = '< x' becomes x - 0.01 ○ Example 2: 1 Significant Digit = '> x' becomes x + 0.1 ○ Example 3: 0 Significant Digits = '< x' becomes x - 1

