16.10.2.2.2. Clinical Response

Presence or absence of clinical response will be described using a conventional logistic regression model. Time to response will be explored using Kaplan Meier plots with exposure subdivided into quartiles and quintiles.

PFS will be explored using Kaplan Meier plots with exposure subdivided into quartiles and quintiles and occurrence of progression may also be described using a conventional logistic regression model.

Duration of response will be explored using Kaplan Meier plots with exposure subdivided into quartiles and quintiles.

Best clinical response will be analyzed using an ordered logistic regression, with response categorized from 0 (progressive disease) to 6 (stringent complete response). Exposure will be treated as a categorical variable subdivided into quartiles and quintiles.

In the ordered logistic regression analyses, the use of categorical measures of exposure in lieu of continuous variables will allow for non-parametric descriptions of response functions.

Best clinical response as assessed by maximum reduction in M-protein or FLC will be analyzed by exposure (continuous and/or by quartile and quintile of exposure).

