Proteasome Inhibitor	5 (5%)	5 (5%)	10 (5%)
BORTEZOMIB	5 (5%)	5 (5%)	10 (5%)
CARFILZOMIB	5 (5%)	5 (5%)	10 (5%)
IXAZOMIB	5 (5%)	5 (5%)	10 (5%)
Chemotherapy	5 (5%)	5 (5%)	10 (5%)
Stem Cell Transplant	5 (5%)	5 (5%)	10 (5%)
Other	5 (5%)	5 (5%)	10 (5%)
Monoclonal Antibody	5 (5%)	5 (5%)	10 (5%)
CXCR4	5 (5%)	5 (5%)	10 (5%)
DARATUMUMAB	5 (5%)	5 (5%)	10 (5%)
ELOTUZUMAB	5 (5%)	5 (5%)	10 (5%)
SILTUXIMAB	5 (5%)	5 (5%)	10 (5%)
HDAC Inhibitor	5 (5%)	5 (5%)	10 (5%)
Not Classified	5 (5%)	5 (5%)	10 (5%)
Immunomodulator and Proteasome Inhibitor	5 (5%)	5 (5%)	10 (5%)

[figure not shown]
This table is summarized per subject level

PPD

Example: POP_F2
Protocol: BMA117159
Population: Part 2 MM

(Data as of: 30MAY2001)

Figure x.xxxx
Plot of Dose Reduction of GSK28557916 by Cycle (Part 2 MM)

[figure not shown]
Doses 1.9 mg/kg and 1.7 mg/kg are combined and represented by 1.7 mg/kg.

PPD

Example: EFF_F1
Protocol: BMA117159
Population: Part 2 MM

Page 1 of 1
(Data as of: 30MAY2001)

Figure 12.0020
Correlation of Free Soluble BCMA at Pre-Dose (Cycle 1) and
Maximum Percentage Change from Baseline
in Serum M-Protein, Urine M-Protein or Serum FLC

Subjid (Treatment) (Type/ Best confirmed Response)
PPD

[figure not shown]
Serum M-protein depicted for subjects with serum M-Protein values;
Urine M-Protein depicted for subjects without serum M-Protein values.
Changes in affected FLC depicted in subjects with no available Serum M-protein values nor Urine M-Protein.

PPD

Example: EFF_F2
 Protocol: BMA117159
 Population: Part 2 MM

Page 1 of 1
 (Data as of: 30MAY2001)

Figure x.xxxx
 Forest Plot - Overall Response Rate (ORR) (Part 2 MM)

[figure not shown]
A subject is considered as high risk if the subject has any of the following cytogenetics:

PPD

Example: EFF_F3
Protocol: BMA117159
Population: Part 2 MM

Page 1 of 1
(Data as of: 30MAY2001)

Figure x.xxxx
Profile Plot of Responders (Part 2 MM)

SCR: Stringent Complete Response, CR: Complete Response, VGPR: Very Good Partial Response, PR: Partial Response.

PPD

Example: SAFE_T1
 Protocol: BMA117159
 Population: Part 1

Page 1 of 1
 (Data as of: 30MAY2001)

Table x.xxxx
 Summary of Subjects Experiencing Corneal Clinical Signs (Part 1)

	0.03 mg/kg (N=10)	0.06 mg/kg (N=20)	Total (N=30)
Number of Subjects Experiencing Corneal Clinical Signs	5 (50%)	15 (75%)	20 (67%)
Corneal Epithelium Finding			
Abnormal, epithelial edema	5 (50%)	12 (60%)	17 (57%)
Abnormal, epithelial edema -subtle epithelial haze	3 (30%)	11 (55%)	14 (47%)

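### The Part 2 MM maximum-reduction plots choose the marker by data availability, not baseline measurability, so some urine- or FLC-measurable subjects can be plotted on a serum value that does not reliably show their response

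*SAP*

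**What the plan says.** Section 7.3.1.3 sets three steps for the waterfall plot:

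- Step 1: "Plot Serum M-protein maximum percent reduction from baseline if data is available".
- Step 2: "If [1] is not feasible, plot Urine M-protein maximum percent reduction from baseline if data is available".
- Step 3: "If both [1] and [2] are not feasible, plot maximum percent reduction from baseline for difference between two types of Serum FLC", again subject to data being there.

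The SAP does not define feasible. The footnotes of shell EFF_F1 in Appendix 13 show the intended reading: "Urine M-Protein depicted for subjects without serum M-Protein values", and "Changes in affected FLC depicted in subjects with no available Serum M-protein values nor Urine M-Protein". The sBCMA scatter plot is told to follow the same order.

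For PFS, footnote 1 of Table 5 (section 7.3.1.2.1) says "adequate baseline assessment is defined as at baseline, a patient has at least one of the following measurements". For Part 2 the alternatives are serum M-protein of at least 0.5 g/dL, urine M-protein of at least 200 mg/24h, involved FLC of at least 5 mg/dL with an abnormal ratio, or a biopsy-proven plasmacytoma. Table 6 repeats this for TTP. For Part 1 no numeric thresholds are given for serum, urine or FLC.

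Section 16.6.3, which names all three markers, converts non-detectable results to numbers: "the number of significant digits in the observed values will be used to determine how much to add or subtract". Section 16.10.2.2.2 adds: "Best clinical response as assessed by maximum reduction in M-protein or FLC will be analyzed by exposure".

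**The concern.** The hierarchy tests whether a value exists. Whether a percent change in a marker means anything depends on how much of that marker was present at baseline. The SAP recognises this for PFS and TTP in Part 2 but not here. The hierarchy is also uneven: step 3 requires an abnormal baseline FLC ratio, while steps 1 and 2 have no such condition.

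Serum M-protein is scheduled for Part 2 MM subjects at screening, at Cycle 2 Day 1 and at each later cycle (section 16.2.3.1), so a serum value will often be on file for a subject whose disease is measurable only in urine or by FLC. At stake is the depth-of-response picture in the waterfall plots (Figures 12.0010 and 12.0011, notably 12.0011) and the sBCMA scatter plots (12.0020 and 12.0021, notably 12.0021). If MAXPRED is built the same way, RESPRATIO in the exposure-response work is also affected. The waterfalls print best confirmed response with the bars, so a flat bar could carry a PR or VGPR label.

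**Working it through.** The plan states no figure on this point, so there is none to reproduce. The check applies the SAP's own rules to illustrative subjects. All patient values below are assumptions.

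**Rules used**

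- Imputation (16.6.3): '<x' becomes x - 0.01 with two digits and x - 1 with none. The one-digit example is written for '>x' (x + 0.1), so by the same pattern '<x' becomes x - 0.1.
- Percent change (7.3.1.3): (post - baseline) / baseline × 100.
- RESPRATIO (16.9.1 and 16.10.1): max((100 + MAXPRED)/100, 0.001).
- Part 2 thresholds (Table 5, footnote 1): serum 0.5 g/dL, urine 200 mg/24h, involved FLC 5 mg/dL (50 mg/L) with an abnormal ratio.

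**Marker chosen by the rule against marker measurable at baseline**

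| Subject | Serum, chosen as written | Result | Measurable marker | Result |
|---|---|---|---|---|
| A, FLC-measurable | '<0.2' throughout: 0.1 to 0.1 | 0%, RESPRATIO 1.00 | FLC difference 500 to 50 mg/L | (50 - 500)/500 = -90%, RESPRATIO 0.10 |
| B, FLC-measurable | '<0.10' throughout: 0.09 to 0.09 | 0%, RESPRATIO 1.00 | FLC difference 500 to 25 mg/L | (25 - 500)/500 = -95%, RESPRATIO 0.05 |
| C, urine-measurable | 0.20 to 0.20 g/dL | 0%, RESPRATIO 1.00 | Urine 1000 to 80 mg/24h | (80 - 1000)/1000 = -92%, RESPRATIO 0.08 |

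**Noise below the threshold**

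- Serum 0.20 to 0.10 g/dL: (0.10 - 0.20)/0.20 = -50%, RESPRATIO 0.50. This lands on one of the waterfall's reference lines.
- Serum 0.10 to 0.20 g/dL: +100%, RESPRATIO 2.00. Because the maximum reduction is plotted, this appears only if no post-baseline value is below 0.20.

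Every serum value here lies under 0.5 g/dL.

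**Who escapes**

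A missing serum baseline, or one of exactly 0, gives no percent change, so step 1 fails and the subject moves to the next marker. Reporting format can decide this: '<0.1' with one digit becomes 0 and falls through to urine, while '<0.10' with two digits becomes 0.09 and keeps serum. The urine step has no threshold either, so the same question can arise between urine and FLC.

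**The case against.** The strongest reply is that the rule does not take serum in every case: step 2 opens when step 1 is not feasible, and a zero or missing baseline opens it. The SAP does not say how the laboratory reports an absent M-spike, and a visit schedule does not prove that a usable numeric baseline exists. That stands. It limits the point to non-zero sub-threshold or imputed serum baselines.

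The Table 5 thresholds were written for PFS censoring, not for choosing a marker. That also stands, but they are the only statement of measurable disease in the SAP and serve as a ready standard. They give no numeric cut-offs for Part 1, so carrying them over there to drop subjects would go beyond the plan.

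A reader might infer more than the document supports in four ways:

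- **That serum cannot show response in these subjects.** A sub-threshold value can move, but not reliably.
- **That a certain number of bars is wrong.** The SAP gives no share of subjects measurable only by urine or FLC, and not all of them would have an affected serum baseline.
- **That the exposure and sBCMA relationships are biased toward no effect.** Flat bars pull one way, but the best of several noisy values can also create false falls, such as the -50% above. The sBCMA plots carry no fitted line or R square, so no relationship is estimated there.
- **That the exposure-response variable is certainly affected.** MAXPRED is taken from the response dataset without reference to 7.3.1.3. It is described as the maximum reduction in M-protein or FLC, RSPTYP codes the same three markers, and no other derivation is given. The link is implied, not stated.

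There is some mitigation. Figure 12.0010 marks the test type by symbol and 12.0011 by shade, both print best confirmed response, and responses by visit are listed, so a mismatch could be noticed. Noticing a wrong marker does not put the right one on the plot.

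**Conclusion.** The concern holds in limited form. As written, 7.3.1.3 can plot 0% for a Part 2 MM subject whose baseline-measurable marker fell by 90% or more, and can plot sub-threshold serum noise as a sizeable fall or rise. This requires a subject measurable only by urine or FLC, with a serum baseline that is non-zero but below 0.5 g/dL or imputed from '<x'. Subjects whose serum baseline is missing or zero are not affected by the serum step.

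Neither the number of subjects nor the direction of any bias can be derived from the SAP. The effect is confined to the exploratory waterfall and sBCMA scatter plots and, on the condition that MAXPRED uses the same hierarchy, to the exposure-response analysis of maximum reduction. ORR, PFS, TTP and DOR rest on investigator-assessed response and progression and do not change.

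**What to change.** **Part 2 MM.** In 7.3.1.3, choose the marker by the Table 5 baseline thresholds in a fixed order:

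1. Serum M-protein if baseline is at least 0.5 g/dL.
2. Otherwise urine M-protein if at least 200 mg/24h.
3. Otherwise the FLC difference if involved FLC is at least 5 mg/dL with an abnormal ratio.
4. Otherwise not plotted, with the number of such subjects in a footnote.

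**Imputed values.** Do not use a value imputed from '<x' as the baseline for a percent change.

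**Part 1.** Keep all subjects on the plot, since the SAP sets no numeric thresholds there, but apply the same restriction on imputed baselines and flag bars whose marker was below the Part 2 thresholds.

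**Consistency.** Align the EFF_F1 footnotes, and state in 16.9.1 and 16.10.1 that MAXPRED, and RSPTYP where it is used, follow the same rule.

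The cost is SAP wording, one derivation rule and shell footnotes. The markers and thresholds are already in the SAP, and no new data are needed. A few Part 2 subjects, such as those measurable only by plasmacytoma, may have no bar. The change should be made before the database freeze, so that the marker is not chosen after the bars have been seen.

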7.3.1.4. Subgroup Analysis of ORR

A forest plot of ORR analysis will be provided for the following subgroups: Age, Sex, Ethnic Background, ISS Staging at Screening, Number of prior lines of therapy, Type of myeloma, Prior Daratumumab Treatment, Refractory to prior anti-cancer therapy, Cytogenetics Risk as defined in Section 5.2.1.

